3.1.2 Lead-In Period

Eligible subjects who complete the qualification period will have Day -28 visit performed and will enter the lead-in period. During the lead-in period, subjects will continue to maintain their stable dose of commercially available OAD, ACEI or ARB and will also continue to maintain their stable dose of an additional commercially available antihypertensive medication.

The lead-in period is a 4-week period during which subjects will receive single-blind placebo. Subjects will be instructed to take all study medication as well as their stable dose of ACEI or ARB and additional hypertensive medication once a day between 6am and 11am, at a similar time each day throughout the study. All medication (including blinded study medication, antihypertensive medications and OAD) must be withheld on the morning of each study visit. Compliance will be assessed based upon subject's interview, review of subject's log and a count of the blinded tablets returned at each visit and its importance will be stressed. The visit must be re-scheduled within 3 days if the study medication was not withheld accordingly.

Subjects will also receive diet and exercise counseling consistent with the American Diabetes Association (ADA) recommendations (or similar local guidelines). A Registered Dietitian, Registered Nurse, Physician, Certified Diabetes Educator, Nutritionist, or other qualified member of the study team who has appropriate documented training will provide this counseling.

Upon entry in the lead-in period Day -28, subjects will also be given a blood glucose meter and instructed on its use by site personnel. Subjects should demonstrate the ability to correctly perform self-monitoring of blood glucose (SMBG) during the lead-in period, as required per protocol (see Section 5.3.1).

A scheduled visit will occur at Day -14 to assess fasting plasma glucose (FPG), seated blood pressure and study compliance. If the subject has a FPG > 270 mg/dl at this visit, FPG will be repeated within one week. If the repeated FPG value is > 270 mg/dl, the subject will be discontinued. If the subject's seated blood pressure, determined from the mean of 3 replicated measurements, is > 180/110 mmHg at this visit,

the subject will be discontinued from the study. No ABPM or randomization procedures will be performed on subjects discontinued from the study at the Day -14 visit.

The lead-in period will also include 24-hr ABPM between Day -7 and Day -1 prior to randomization. The 24-hr ABPM should be initiated upon completion of all other lead-in visit procedures including administration of the single-blind study medication and between 6am and 11am to ensure trough BP measurements are obtained. Subjects should be instructed to withhold all medication (including blinded study medication, antihypertensive medications and OAD) on the morning of the study visit and to bring their medication to the visit with them. Once the ABPM cuff is in place, the subject should be instructed to take all morning medication while in the office. Initiation of the 24-hour ABPM must be re-scheduled within 3 days if the study medication was not withheld accordingly.

Note: If subjects are taking an additional antihypertensive medication (a (thiazide or thiazide-like diuretic, calcium channel blocker, beta blocker or alpha adrenergic blocker) that is dosed BID, the subject should take their evening dose at their normal daily time while the ABPM cuff is in place (ie, 12 hours \pm 3 hours after the morning medication taken in the office).

The subjects should be scheduled to return to the site following completion of the 24-hr ABPM recording and instructed to withhold all morning medication (including blinded study medication, all antihypertensive medications and OAD) until the ABPM cuff is removed. The 24-hr ABPM data will be downloaded and immediately reviewed and assessed upon transmission. In the event of inadequate data collection (see Section 5.4.2.1), the 24-hr ABPM must be repeated and confirmed as adequate prior to scheduling the randomization visit.

Single-blind placebo will be used to assess subject's compliance with treatment. Subjects should demonstrate good compliance with study medication ($\geq 70\%$ and $\leq 130\%$) during the lead-in period to be eligible for entry into the double-blind treatment period. For subjects with a compliance between $\geq 70\%$ AND < 80% or > 120% AND $\leq 130\%$, the Investigator should ensure that there is no systematic factor which may result in unacceptable compliance with study medication during the treatment period of the

Dapagliflozin MB102077 BMS-512148 Clinical Protocol

trial. Such cases should be discussed with the Medical Monitor prior to randomization.

The lead-in period should be completed in 4 weeks \pm 5 days.

3.1.3 Double-Blind Treatment Period

Following completion of the lead-in period, eligible subjects will enter into the randomized, double-blind, treatment period. Subjects will continue to maintain their stable dose of commercially available OAD, ACEI or ARB and additional antihypertensive medication. Subjects should also continue to take single-blind lead-in study medication throughout any randomization procedures performed on days prior to Day 1 randomization.

Randomization Visit

The first dose of double-blind study medication should only be administered on Day 1 AFTER ALL randomization visit procedures have been completed.

On Day 1, following completion of ALL randomization visit procedures, the IVRS will randomly assign subjects in a 1:1:1:1 ratio to receive one of the following double-blind treatment regimens:

- Dapagliflozin 2.5 mg QD
- Dapagliflozin 5 mg QD
- Dapagliflozin 10 mg QD
- Placebo QD

Subjects will be randomized globally within strata according to their additional antihypertensive medication use (thiazide or thiazide-like diuretics versus calcium channel blockers, beta blockers or alpha adrenergic blockers).

Subjects will be instructed to take all study medication as well as their stable dose of ACEI or ARB and additional hypertensive medication once a day between 6am and 11am, at a similar time each day throughout the study. If subjects are taking an additional

antihypertensive medication that is dosed BID, the subject should continue to take the evening dose at the normal daily time throughout the study (ie, 12 hours \pm 3 hours after the morning medication is taken).

All medication (including blinded study medication, all antihypertensive medications and OAD) must be withheld on the morning of each study visit. Compliance with the daily dosing schedule will be evaluated by subject interview at each visit and its importance will be stressed. The study visit must be re-scheduled within 3 days if the study medication as well as the stable dose of ACEI or ARB and additional antihypertensive medication was not taken between 6am and 11am on the day preceeding the study visit and withheld the morning of the study visit, as instructed.

Dose titration of double-blind study medication is not permitted at any time during the treatment period. In addition, the stable dose of a commercially available OAD, ACEI or ARB and additional antihypertensive medication should remain unchanged for the entire duration of the study.

Double-Blind Treatment Period Visits:

Following randomization, subjects will be followed for a total of 12 weeks on double-blind study medication. Scheduled visits will occur at Weeks 2, 4, 8, and Week 12/Early Termination (ET).

Subjects who discontinue prematurely from the double-blind treatment period will have all Week 12/ET procedures completed prior to discontinuation.

Similar to the randomization visit procedures, Week 12/ET visit procedures should preferably be completed on the same day when possible, or on consecutive days, or, in subjects unavailable on consecutive days, no more than 1 day apart. The Week 12/ET procedures will include 24-hr ABPM (to be conducted within 1 week prior to the Week 12/ET visit). Initiation of the 24-hr ABPM should begin between 6am and 11am to ensure trough BP measurements are obtained. Subjects should be instructed to withhold all medication (including blinded study medication, all antihypertensive medications and OAD) on the morning of the study visit and bring their medication to the visit with them. Once the ABPM cuff is in place, the subject should be instructed to take all medication

while in the office. Initiation of the 24-hour ABPM must be re-scheduled within 3 days if the study medication was not withheld accordingly.

The subjects should be scheduled to return to the site following completion of the 24-hr ABPM recording and to withhold morning medication (including blinded study medication, all antihypertensive medications and OAD) until the ABPM cuff is removed.

The 24-hr ABPM data will be downloaded and immediately reviewed and assessed upon transmission. In the event of inadequate data collection (see Section 5.4.2.1) the 24-hr ABPM must be repeated and confirmed as adequate prior to completing the Week 12/ET visit. Subjects must remain on study medication through the completion of the 24-hr ABPM and Week 12/ET procedures.

[figure not shown]
3.1.4 Follow-Up Visit

Following the 12 week double-blind treatment period subjects will be seen 1 week later for a scheduled Week 13 visit. This will be the conclusion of the study once all procedures are completed. During the follow-up period, subjects will not take any blinded study medication but will continue to maintain their stable dose of a commercially available OAD, ACEI or ARB and additional antihypertensive medication.

3.1.5 Study Schematic

Figure 3.1.5 Study Schematic

Qualification Period	4 - Week Single-	12 Week Double-Blind Treatment Period	1 - Week Follow - up
≤ 14 Days	Blind Placebo Lead-In Period	 *Dapagliflozin 2.5 mg QD *Dapagliflozin 5 mg QD *Dapagliflozin 10 mg QD 	Period (no blinded study medication)
		*Placebo QD	

^{*} Subjects will also take their stable dose of commercially available OAD plus ACEI or ARB and an additional antihypertensive medication with their blinded medication.

3.2 Post Study Access to Therapy

At the end of the study, the sponsor will *not* continue to supply study drug to subjects/investigators unless the sponsor chooses to extend the study. The investigator should ensure that the subject receives appropriate standard of care to treat the condition under study.

^{**24-}hr Ambulatory Blood Pressure Monitoring (ABPM) during lead-in must be conducted between days -7 and -1, *prior* to randomization.

^{***24}hr ABPM during Double-Blind period must be completed within 1 week prior to the Week 12/ET visit.

3.3 Study Population

For entry into the study, the following criteria MUST be met.

3.3.1 Inclusion Criteria

Signed Written Informed Consent

1) Subjects must be willing and able to give signed and dated written informed consent.

Target Population

- 2) Subjects must have type 2 diabetes with inadequate glycemic control, defined as central laboratory HbA1c \geq 7.0% and \leq 10.0% obtained at the enrollment visit.
 - Note: A one-time central laboratory re-test of the HbA1c is allowed in subjects with an initial central laboratory HbA1c of 6.9% or 10.1% who are otherwise eligible, as determined by the Investigator.
- 3) Subjects must be on a stable dose of an OAD for at least 6 weeks (12 weeks for a TZD) prior to enrollment, stable doses of an ACEI or an ARB and one additional antihypertensive medication (either a thiazide or thiazide-like diuretic or a calcium channel blocker, beta blocker or alpha adrenergic blocker) for at least 4 weeks. Stable dose is defined as a dose that has remained the same for the specified number of weeks, as mentioned above, prior to the enrollment visit (ie, same prescribed total daily dose).

Note: Subjects treated with more than one OAD (combination OAD medications) will be allowed as long as the doses of the combination OAD medications have been stable for the specified number of weeks.

- Also refer to prohibited and/or restricted treatments section 3.4.1.
- 4) Subjects must have inadequately controlled hypertension, defined as seated SBP ≥ 140 and < 165 mmHg AND seated DBP ≥ 85 and < 105 mmHg, each representing the mean of three consecutive determinations, evaluated at both the enrollment and **Day -1 visits**.
 - Enrollment Visit Only: If the mean seated BP value obtained at enrollment visit does not meet the above definition, a one-time retest of seated BP within 3 days may be allowed, as determined by the Investigator, prior to the Day 1 visit.
- 5) C-peptide $\geq 0.8 \text{ ng/mL} (0.30 \text{ nmol/L}).$
- 6) BMI $\leq 45.0 \text{ kg/m}^2$ at the enrollment visit.

Age and Reproductive Status

7) Men and women ages must be ≥ 18 and ≤ 89 years old at the time of the enrollment visit. Men and women of childbearing potential (WOCBP) must be using an

acceptable method of contraception to avoid pregnancy throughout the study in such a manner that the risk of pregnancy is minimized. See Section 3.3.3 for the definition of WOCBP.

WOCBP must have a negative serum or urine pregnancy test (minimum sensitivity 25 IU/L or equivalent units of HCG) within 72 hours prior to the start of investigational product. Women must not be breastfeeding

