Subjects must have inadequate BP control, defined as systolic BP (SBP) \geq 140 and < 165 mmHg, AND diastolic BP (DBP) \geq 85 and < 105 mmHg at the enrollment and Day 1 visits while on a stable dose of ACEI or ARB, and an additional antihypertensive medication (thiazide/thiazide-like diuretic or calcium channel blocker, beta blocker, alpha adrenergic blocker) for at least 4 weeks prior to the enrollment visit.

^{**24-}hr Ambulatory Blood Pressure Monitoring (ABPM) during lead-in must be conducted between days -7 and -1, *prior* to randomization.

^{***24}hr ABPM during Double-Blind period must be completed within 1 week prior to the Week 12/ET visit.

All OAD, ACEI or ARB and additional antihypertensive medications will be commercially available and will not be supplied by Bristol-Myers Squibb.

Subjects must also have a Body Mass Index (BMI) $\leq 45.0 \text{ kg/m}^2$ as well as a central laboratory enrollment C-peptide value of $\geq 0.8 \text{ ng/mL}$ (0.30 nmol/L)

Key Exclusion Criteria Include:

- AST > 3X ULN
- ALT > 3X ULN
- Serum total bilirubin (TB) ≥ 1.5X ULN
- Serum Creatinine $(S_{Cr}) \ge 2.0$ mg/dL unless subject is on metformin then the exclusionary limits will be $S_{Cr} \ge 1.50$ mg/dL (133 mmol/L) for male subjects; $S_{Cr} \ge 1.40$ mg/dL (124 mmol/L) for female subjects
- Estimated creatinine clearance (Crcl) of < 50ml/min

Study Assessments and Primary Endpoint: The co-primary endpoints are the change in seated systolic blood pressure from baseline at Week 12, or the last post-baseline measurement prior to Week 12 if no Week 12 assessment is available, and the change in HbA1c from baseline at Week 12, or the last post-baseline measurement prior to Week 12 if no Week 12 assessment is available.

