APPENDIX 2 CENTRAL LABORATORY ASSESSMENTS

Blood and urine samples will be obtained at specified time points for laboratory evaluations. The central laboratory for this study will perform the analysis of all scheduled laboratory tests and will provide reference ranges for these tests. All samples for clinical laboratory testing must be collected in the morning after the subject has fasted for at least 8 hours prior to collection. The detailed methods for specimen collection, handling, processing, shipping, and storage will be supplied in the Investigator's Laboratory Manual provided by the Central Laboratory. All clinical laboratory tests will be performed by the Central Laboratory or designated reference laboratory.

During the lead-in and double-blind treatment periods, the HbA1c values will be masked/blinded to the Investigator and to the Sponsor. These values will be provided to the Investigator after the study has been completed.

During the lead-in, double-blind treatment periods, the urinary glucose values, including the urinary glucose:creatinine ratio, will be masked/blinded to the Investigator and to the Sponsor. The urinary glucose values will be provided to the Investigator after the study has been completed.

The following sections indicate the laboratory tests required for this study. For countries using conventional units, the results will be reported using conventional units. For countries using SI units, the results will be reported using SI units. In cases of differences in the units as listed in this protocol compared to the units on the central laboratory reports, the units from the central laboratory reports will be used.

PROTOCOL-SPECIFIC CENTRAL LABORATORY ASSESSMENTS:

- HbA1c (%)
- FPG (mg/dL, mmol/L)
- Fasting C-peptide (ng/mL, nmol/L)
- Fructosamine (µmol/L)
- Fasting serum lipid profile:
 - Total-C (mg/dL, mmol/L)
 - Calculated LDL-C (mg/dL, mmol/L)
 - ◆ Reflex testing will occur for Direct LDL-C if TG > 400 mg/dL (4.52 mmol/L)
 - HDL-C (mg/dL, mmol/L)
 - TG (mg/dL, mmol/L)

Enrollment-Specific Safety Panel

- Hepatitis Screen Panel:
 - Anti-hepatitis C virus antibody
 - ♦ Reflex Testing: If positive, a reflex RIBA HCV will be obtained
- Hepatitis B surface antigen
- TSH (uIU/mL, mIU/L)
 - Reflex Testing: Abnormal TSH value at enrollment will be further evaluated by free T4 (ng/dL, pmol/L).

Specialized Liver Panel

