- 2) Synopsis: Study Design and Schematic: Add inclusion of a stable dose of insulin as monotherapy or in combination with an Oral Antidiabetic agent (OAD). Also added insulin reduction instructions according to HbA1c values throughout the study period. Added randomizing globally within strata for insulin use at baseline.
- 3) Synopsis: Study population: changing HbA1c upper range to 10.5 % and added inclusion of insulin.
- **4)** Synopsis: Key Exclusion criteria, change estimated creatinine clearance (Crcl) to < 60 ml/min.
- 5) Synopsis: Statistical methods: Removal of the 5.0 mg dapagliflozin dose arm and decreased number of randomized subjects from 765 to 722, reduced treatment arms from 4 to 2 and changed individual treatment arms to 361 subjects. Removed paragraph explaining use of Bonferroni's adjustment.
- 6) Protocol sections: Study Rationale 1.1, Objectives 1.3 (primary 1.3.1, secondary 1.3.2 and exploratory 1.3.3), Study Design and Duration 3.1, Qualification Period 3.1.1, Lead-In Period 3.1.2, Double Blind Treatment Period (Randomization Visit) 3.1.3, Study Schematic 3.1.5, Inclusion criteria 3.3.1, Study Treatments 4.1 and Table 4.1 B, Investigational Product 4.1.1, Method of Assigning Subject Identification 4.2, Dose Modifications 4.3.1, Efficacy Assessments 5.4 (Primary Efficacy Assessments 5.4.1, and Secondary Efficacy Assessments 5.4.2, Exploratory Efficacy Assessments 5.4.3.
 - a) removal of the dapagliflozin 5.0 mg dosing arm

- b) change in upper limit of HbA1c to 10.5%
- c) change in total number of randomized subjects
- d) change in randomization scheme to 1:1
- e) added global stratification for insulin use
- f) added insulin inclusion and information regarding insulin adjustments during the study period.
- g) changes to inclusion criteria 2, (increase upper limit of HbA1c to 10.5% and allow retest for HbA1c of 10.6 %) and criteria 3, allowing subjects who are on insulin.
- h) add 1 exploratory objective
- 7) Table 1.4.3: Summary of Ongoing, Randomized, Double-blind Phase 2b and 3 Studies: updated table with current information.
- 8) Section 1.5, Overall Risk/Benefit Assessment: updated section with current information.
- 9) Added sub-section 3.1.3.1 entitled: Algorithm for Insulin dose reduction by 25% in subjects who are on insulin therapy and have an HbA1c measurement of 7.0 7.4% at enrollment.

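### The C-peptide entry threshold is printed as two unequal values, 0.8 ng/mL and 0.30 nmol/L, and nothing shown says which one binds

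*Supplement*

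**What the plan says.** Section 3.3.1, criterion 5, reads "C-peptide $\geq 0.8 \text{ ng/mL} (0.30 \text{ nmol/L". The Synopsis, under Study Population, gives the same pair: "enrollment C-peptide value of $\geq 0.8 \text{ ng/mL}$ (0.30 nmol/L". In both places the nmol/L figure stands in brackets as the equivalent of the ng/mL figure.

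Appendix 2 lists the test in both units, "Fasting C-peptide (ng/mL, nmol/L". On reporting it says "For countries using conventional units, the results will be reported using conventional units" and "For countries using SI units, the results will be reported using SI units". Where the protocol's units differ from those on the report, "the units from the central laboratory reports will be used".

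Section 3.3.2 requires every eligibility criterion to be fully met. Section 3.3.1 allows re-tests for HbA1c and enrollment blood pressure, but mentions none for C-peptide.

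The change lists shown for Amendments 02, 07, 08 and 09 contain no correction to the C-peptide figures. Amendment 02 (item 3) names inclusion criterion 5, but the change described is the ambulatory blood pressure requirement. Amendment 07 corrected a unit error in the creatinine exclusion and no other laboratory threshold.

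**The concern.** A threshold printed in two units should be one concentration written twice. If the two figures differ, a subject between them meets the criterion on one reading and fails it on the other. Randomization is global and results come back in the country's own unit system, so the reading could follow the country. The result would be inconsistent screening decisions: some subjects turned away, or some admitted, against whatever limit the sponsor intended. An error of this kind is easy to miss, because 0.30 nmol/L is a plausible-looking number that a site would simply apply.

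**Working it through.** **Inputs from the documents.** 0.8 ng/mL and 0.30 nmol/L (Synopsis; Section 3.3.1, criterion 5).

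**Assumed input.** Molar mass M of human C-peptide. The documents do not give it. Summing residue masses for the 31-residue peptide gives 3020 g/mol; the range tried is 3000 to 3050 g/mol.

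**Formula.** nmol/L = (ng/mL) × 1000 / M, and the reverse, ng/mL = (nmol/L) × M / 1000.

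**Step 1: try to reproduce the printed pair.** The pair agrees only if M = 0.8 × 1000 / 0.30 = 2667 g/mol, which is outside the assumed range.

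**Step 2: convert each figure.**

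| M (g/mol) | 0.8 ng/mL in nmol/L | 0.30 nmol/L in ng/mL | 0.30 ÷ converted value |
|---|---|---|---|
| 3000 | 0.267 | 0.900 | 1.125 |
| 3020 | 0.265 | 0.906 | 1.133 |
| 3050 | 0.262 | 0.915 | 1.144 |

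**Step 3: allow for rounding at the printed precision.** Let 0.8 stand for 0.75 to 0.85 and 0.30 for 0.295 to 0.305. The implied molar mass then runs from 0.75 × 1000 / 0.305 = 2459 to 0.85 × 1000 / 0.295 = 2881 g/mol, still below 3000. Holding 0.8 exact and rounding only the SI figure, at M = 3020, the ratio runs from 0.295 / 0.265 = 1.11 to 0.305 / 0.265 = 1.15.

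**Step 4: a control on the protocol's other dual-unit figures.** For creatinine the protocol supplies its own factor: 0.50 mg/dL is given as 44.2 µmol/L, so 88.4 per mg/dL.

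- Creatinine: 1.50 × 88.4 = 132.6 (printed 133); 1.40 × 88.4 = 123.8 (printed 124); 2.0 × 88.4 = 176.8 (printed 176).
- Glucose, with an assumed 18.016 mg/dL per mmol/L: 50 gives 2.78 (printed 2.8) and 54 gives 3.00 (printed 3).
- Triglycerides, with an assumed 88.57 mg/dL per mmol/L: 400 gives 4.516 (printed 4.52).

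All of these agree within 1%. C-peptide is the outlier.

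**Step 5: what it means for one subject.** A value of 0.85 ng/mL is 0.85 × 1000 / 3020 = 0.281 nmol/L. It lies above 0.8 ng/mL and below 0.30 nmol/L, so the two printed limits give opposite answers.

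**The case against.** **Rounding.** The correct conversion, 0.265, rounds to 0.3 at one decimal, and 0.30 may be that figure with a trailing zero added. Treated as a one-decimal figure (0.25 to 0.35), the pair is compatible with molar masses from 0.75 × 1000 / 0.35 = 2143 to 0.85 × 1000 / 0.25 = 3400 g/mol, which includes 3020. This may well be how the figure arose. It does not remove the difficulty, because a site comparing a result with the printed 0.30 uses 0.30.

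**The country effect.** A reader might infer that SI-unit countries do apply a cut-off about 13% stricter. The documents do not show that. Appendix 2 fixes the units on the report, not the figure against which eligibility is judged. The Synopsis asks for a "central laboratory enrollment C-peptide value of", and the ng/mL figure comes first with the SI figure in brackets. A central laboratory flagging against one fixed value would remove the difference. But no text shown provides for such a flag, so different cut-offs remain possible without being demonstrated.

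**Version.** The wording comes from the original protocol. The full revised protocol after Amendment 09 and Amendments 03 to 06 are not shown, so the figure may have been mended there. That stands as a limit on confidence. It does not defeat the point, since no change list shown corrects the value.

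**Consequence.** A reader might go further and see a threat to the HbA1c co-primary endpoint, or a larger effect since Amendment 08: "Add inclusion of a stable dose of insulin as monotherapy or in combination with an Oral Antidiabetic agent (OAD". Neither is supported. The criterion acts before randomization and alike for every arm. The documents give no C-peptide distribution, for insulin users or anyone else, and no insulin-user share, so any percentage affected would rest on invented inputs.

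**Conclusion.** The point holds as an inconsistency in an entry criterion. The two printed values differ by 12.5% to 14.4% over the assumed molar-mass range, rounding at the printed precision does not explain the gap, and no text shown says which value binds. A subject between about 0.80 and 0.91 ng/mL could be classed differently depending on the unit in which the result is read.

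It is a minor fault. It concerns a narrow band at screening and leaves the treatment contrast, power and Type I error unaffected; how many subjects fall in the band cannot be determined. The conclusion rests on the assumed molar mass and, for the country effect, on sites using the figure printed in their own unit. Confidence that the fault survives in the current text is moderate only.

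**What to change.** The sponsor should reconcile the two values: state which one is binding, and derive the other from it with a stated conversion factor and enough decimals that both describe the same limit. Which value is intended is for the sponsor to say. The correction belongs in the Synopsis and in the C-peptide criterion of Section 3.3.1, which may have been renumbered after Amendment 02, and should be checked against the current revised protocol. The central laboratory should flag eligibility against that single value in both unit systems.

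The cost is one corrected figure in two places and one laboratory flag setting, with no additional subjects, visits or procedures.
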